Title: The safety and effectiveness of clinical performance of Breath-O correct orthokeratology lenses

(NCT03616600)

Date: 10th March, 2019

Title: The safety and effectiveness of clinical performance of Breath-O correct orthokeratology lenses

Methods:

Sample size: 15 subjects for each group were recruited

Groups: Treatment group – prescription of Breath-O Correct lens Control group – non-contact lens wearer

Inclusive criteria:

Age: 18 to 30 years

Refractive error: Spherical: normally -1.00D to -4.00D (maximum up to -5.00D); Cylindrical: normally \leq half of Sph (against-the-rule Astig.: \leq -0.75D) (maximum up to \leq -1.50D)

Best corrected Visual acuity: monocular ETDRS 0.0 or better

Ocular health: No ocular abnormality, no contra-indications for overnight orthokeratology lens wear, no refractive surgery

General health: No systemic diseases

Requirement: No history of orthokeratology lenses wearing. Agree to participate in this study and willing to wear the orthokeratology lenses overnight in accordance with the instructions given and to come back for follow up within the study period

Parameters to be assessed:

Effectiveness: Objective and subjective refractive error, central corneal thickness, high contrast visual acuity, low contrast visual acuity, corneal topography

Safety: Corneal epithelium and endothelium health, corneal resistance factor and corneal hysteresis, tears quality.

Subjective evaluation: OSDI Questionnaire

Analysis: Categorical variables were presented as number or percentage, while continuous variables were presented as mean and standard deviation. Data from both eyes of each subject were analyzed for follow-up visits (within subjects) and for group comparison (between groups). RM-ANOVA, 2-way ANOVA and Friedman test were used for comparison. The significance level is set at p<0.05.

Protocol:

- All the subjects had a baseline eye examination with all the above tests. A written consent was obtained from each eligible subject before randomly allocating into treatment group (fitting of the contact lenses) or control group (no fitting of contact lens)
- A pair of Breath-O Correct lenses were prescribed for each eligible subject of the treatment group with full wearing instructions of orthokeratology
- After successful prescription of the lenses, the subjects of the treatment group came back for regular visits listed in Figure 1

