- For the subjects of the control group, all had the eye examination same as those received by treatment group at the time point of baseline, 1st month and 3rd month.

[figure not shown]

Figure 1. Schedule of visits

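### The named within-subject tests (RM-ANOVA, Friedman) use only subjects seen at every visit, so if poor tolerance leads to missed visits, the tested changes could favour those who continued

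*Combined protocol and SAP*

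**What the plan says.** The Analysis paragraph under Methods assigns the data to two uses: "Data from both eyes of each subject were analyzed for follow-up visits (within subjects) and for group comparison (between groups". It then lists the tests: "RM-ANOVA, 2-way ANOVA and Friedman test were used for comparison". The tests are not matched to individual outcomes, but RM-ANOVA and Friedman are the two suited to comparing visits within a subject.

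The same paragraph gives the descriptive summaries: "Categorical variables were presented as number or percentage, while continuous variables were presented as mean and standard deviation". It does not restrict them to subjects with complete follow-up.

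On visits, the third Protocol bullet says that "the subjects of the treatment group came back for regular visits listed in Figure 1"; that figure is not shown in the text available. The last bullet places the control examinations "at the time point of baseline, 1st month and 3rd month". The first bullet says that every subject had the baseline examination.

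On size, the plan says "Sample size: 15 subjects for each group were recruited". The text has no rule for missed visits, no analysis population, no imputation, no handling of subjects who stop lens wear, and no dropout figure.

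**The concern.** Both within-subject tests compare visits inside complete rows of data. If a treated subject has a poor corneal or tear finding early and does not return for a later visit, the tests in standard form cannot use that subject, and the usual remedy is to drop the whole row. The early finding was observed, yet it does not enter the test.

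This matters because safety is half of the title question, and the listed outcomes ("Safety: Corneal epithelium and endothelium health, corneal resistance factor and corneal hysteresis, tears quality", with OSDI as the subjective measure) are plausible reasons for giving up an overnight lens. If absence is related to those outcomes, the subjects who leave the test are the ones who carry the signal. The tested worsening would then tend to look too small, and the tested effectiveness would lean towards subjects who continued. The 2-way ANOVA in ordinary form would keep the same subject's early rows, so the named tests could describe different sets of subjects without the report saying so. With 15 per group, one or two subjects are a noticeable share.

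**Working it through.** The plan gives no power, SD or dropout figure, so there is nothing of its own to reproduce. From the plan: 15 subjects per group, the three named tests, and control visits at baseline and at months 1 and 3 (2 follow-up visits). Everything else below is an assumption.

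**1. Do the named tests drop incomplete subjects?** A simulated set of 15 subjects by 4 visits (60 values) was given one missing visit in each of two subjects.
- A standard RM-ANOVA routine refused the data as unbalanced.
- A standard Friedman routine gave no result until the two subjects were removed, leaving 13 subjects and 13 × 4 = 52 values.
- A mixed model kept all 15 subjects and 60 − 2 = 58 values.

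**2. How many subjects might be lost?** Baseline was done in everyone, so only follow-up visits can be missed. With a chance m of missing each of k follow-up visits independently, the share deleted is 1 − (1 − m)^k.
- k = 2, m = 0.05: 1 − 0.95² = 9.8%, leaving 15 × 0.9025 = 13.5 complete subjects.
- k = 4: 1 − 0.95⁴ = 18.5%. k = 5: 1 − 0.95⁵ = 22.6%. These apply only if the treated schedule is that long, which the available text does not show.
- Chance of at least one dropout among 15 treated subjects: 1 − 0.95¹⁵ = 54% at an assumed 5% dropout, and 1 − 0.90¹⁵ = 79% at 10%.

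**3. How large could the bias be?** Assume a normal outcome with SD 1, a true worsening of 0.50 SD at every follow-up, and the worst fraction q at the first follow-up never returning. Let ρb be the correlation of follow-up with baseline, and ρf the correlation between follow-up visits. Among completers the first follow-up mean is lowered by s = φ(z)/(1 − q), where z cuts off the top fraction q. Baseline is lowered by ρb·s and later visits by ρf·s. The complete-case changes are therefore:
- first follow-up: 0.50 − s(1 − ρb)
- last follow-up: 0.50 − s(ρf − ρb)

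For q = 0.20, s = φ(0.842)/0.80 = 0.280/0.80 = 0.350.

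| ρb, ρf | First follow-up | Last follow-up |
|---|---|---|
| 0.5, 0.5 | 0.50 − 0.350 × 0.5 = 0.325 | 0.50 |
| 0.5, 0.7 | 0.325 | 0.50 − 0.350 × 0.2 = 0.43 |
| 0.3, 0.7 | 0.50 − 0.350 × 0.7 = 0.255 | 0.50 − 0.350 × 0.4 = 0.36 |
| 0.5, 0.8 | 0.325 | 0.50 − 0.350 × 0.3 = 0.395 |

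Simulation agrees to rounding: 0.25 to 0.32 SD at the first follow-up and 0.36 to 0.50 SD at the last. For q = 0.10, s = 0.1755/0.90 = 0.195, and the first-visit change is 0.50 − 0.195 × 0.7 = 0.36 to 0.50 − 0.195 × 0.5 = 0.40.

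**4. Would a mixed model repair it?** This depends on the covariance. In the q = 0.20 scenarios, an estimate that lets visit correlations differ returns 0.50 SD at the last visit. A random-intercept model, which forces equal correlation between all visits, recovers 0.50 at the first follow-up. At the last follow-up it gives about 0.45, 0.40 and 0.42 SD for (0.5, 0.7), (0.3, 0.7) and (0.5, 0.8), where complete cases give 0.43, 0.36 and 0.39. Most of the last-visit bias remains.

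**The case against.** The strongest reply is that the plan never says incomplete subjects are deleted. Deletion is the default of the named tests, and nothing rules out imputation or an all-data fit. That is fair, but no such step is named either.

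Second, a reader might infer that a treated subject who misses a visit loses all data, or that the treatment-arm safety result describes only those who tolerated the lens. The documents do not support this. The counts, percentages, means and SDs are not limited to completers, and the 2-way ANOVA keeps early rows. Nor is stopping the lenses the same as missing a visit: a subject who stops but attends every examination stays in every test.

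Third, no dropout is reported. The text says in the past tense that treated subjects returned and that all controls were examined. This does not establish full attendance, but if attendance was full the point has no effect.

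Fourth, a reader might infer that deletion falls more heavily on the lens arm. That requires a longer treated schedule, which rests on a figure not shown.

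Fifth, the bias figures come from a constructed extreme in which absence is fully determined by one early value. They are upper-end illustrations, and the last-visit bias vanishes when all correlations are equal.

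All five limit the point. None supplies a way for an incomplete subject to enter the within-subject tests.

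**Conclusion.** The point holds in a limited form and is worth a cheap change. The within-subject tests default to complete cases, and nothing in the plan keeps incomplete subjects in them. The consequence is conditional: someone must miss a visit, and the absence must be related to tolerance for the tested changes to be biased rather than merely less precise.

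Under the assumed extreme case, a true 0.50 SD worsening would be understated by about 35% to 49% at the first follow-up (0.175/0.50 to 0.245/0.50). At the last it would be understated by 0% to 28% (0.14/0.50). With purely random misses at an assumed 5% per visit, about one subject in ten is deleted over two follow-up visits. None of these rates or correlations comes from the documents. The finding concerns the tested changes only; it does not show that safety findings are hidden from the report as a whole.

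**What to change.** In Analysis:

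- **Continuous outcomes.** Replace RM-ANOVA with a mixed model for repeated measures using all observed visits of every randomised subject, including visits before lens wear stopped. Take visit as a categorical factor, and add group and group-by-visit at baseline, month 1 and month 3 for the between-group comparison. Link both eyes within subject. Use an unstructured or otherwise unequal visit covariance with a small-sample degrees-of-freedom correction. Name a random-intercept-only model solely as a stated fallback, because it leaves part of the last-visit bias.
- **Graded safety findings.** Report them by visit on all available data. Tabulate the last observed grade of each treated subject who stopped, with all 15 treated subjects as denominator. The Skillings-Mack test may replace Friedman so that incomplete subjects are used, but it does not itself remove bias from outcome-related absence, so the table is still needed.

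The cost is wording and some programming, with no new visits, subjects or procedures. There are two downsides. The model assumes that missingness is predictable from observed values, which is weaker than what a complete-case analysis needs but is still an assumption. An unstructured covariance may also be hard to fit with 15 per arm, which is why the fallback should be written down in advance.

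### The 2-way ANOVA for the group comparison has no stated subject term; run literally as group by visit, it would treat three visits of one subject as independent

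*Combined protocol and SAP*

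**What the plan says.** The Analysis paragraph under Methods lists three tests in one sentence: "RM-ANOVA, 2-way ANOVA and Friedman test were used for comparison". The sentence before it sets out two purposes: "Data from both eyes of each subject were analyzed for follow-up visits (within subjects) and for group comparison (between groups"). No test is assigned to either purpose or to any endpoint. The two factors of the 2-way ANOVA are not named, and no subject term, random effect or within-subject error is mentioned for it.

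On design, Methods states that "15 subjects for each group were recruited", with random allocation. The Protocol section has the control group examined like the treatment group "at the time point of baseline, 1st month and 3rd month". The two groups therefore share three visits, the first of them before any lens is worn. On testing, "The significance level is set at p<0.05". No standard deviation, expected effect, power or between-visit correlation is given.

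**The concern.** With two groups and three shared visits, group and visit are the obvious two factors. RM-ANOVA and the Friedman test are repeated-measures methods and suit the within-subject comparison over visits. That leaves the 2-way ANOVA as the natural candidate for the comparison between groups. Because it is named apart from RM-ANOVA, its literal form is the one with a single pooled residual and no subject term.

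That form counts three visits of one subject as three independent subjects, and it goes wrong in two directions. The group main effect is judged against too small an error, because stable differences between subjects do not average out over visits as the model supposes. The group by visit interaction, which carries the treatment effect, is judged against too large an error, because those stable differences stay in the residual although they cancel out of the interaction.

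Which harm follows depends on the term that is read as the treatment test. If it is the group main effect, a chance imbalance between 15 and 15 subjects can pass for a lens effect. If it is the interaction, a moderate change in a safety measure such as corneal hysteresis or tear quality can be missed.

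**Working it through.** **Inputs from the documents.** 15 subjects per group; 3 visits shared by both groups; significance level 0.05. The plan states no power or effect size, so there is no figure of its own to reproduce.

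**Assumptions.** Between-visit correlation rho of 0.5 to 0.9, with lower values shown for range; equal correlation between all pairs of visits; one value per subject per visit; shifts in units of the total SD. None of these is in the documents.

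**Group main effect, analytic.** Let the total variance be s². A group mean over 15 × 3 = 45 values has true variance s²(1 + 2·rho)/45. The ANOVA without a subject term assumes s²/45. Its residual has 2 × 3 × 14 = 84 degrees of freedom, so the critical value is sqrt(F(1,84)) = 1.989. The false-positive rate is approximately 2·(1 − Phi(1.989/sqrt(1 + 2·rho))):

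- rho 0.5: 1.989/sqrt(2.0) = 1.406, giving 16.0%
- rho 0.7: 1.989/sqrt(2.4) = 1.284, giving 19.9%
- rho 0.9: 1.989/sqrt(2.8) = 1.188, giving 23.5%

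**Interaction, direction of the error.** Under the null, the interaction mean square has expectation s²(1 − rho), but it is divided by a residual with expectation s². The test is therefore conservative, and more so as rho rises.

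**Simulation** (40,000 null trials and 10,000 trials per power setting; the rho 0.9 power without a subject term was re-run with 100,000). Power is for a 0.8 SD shift present at both month 1 and month 3.

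| rho | Group effect, false positives, no subject term | Interaction, false positives, no subject term | Interaction power, no subject term | Interaction power, subject in model |
|---|---|---|---|---|
| 0.5 | 16.4% | 0.37% | 22% | 59% |
| 0.7 | 20.4% | 0.03% | 16% | 82% |
| 0.9 | 24.3% | about 0 | 7% | over 99% |

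With subject as the error term (28 degrees of freedom for group, 56 for interaction), false positives were 4.7-5.2% for group and 4.7-5.3% for interaction at every rho tried.

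**How far the figures move.**

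- Lower correlation: group false positives are 9.7% at rho 0.2 and 12.0% at 0.3.
- Two visits instead of three: 11.3% to 15.7% for rho 0.5 to 0.9.
- First-order autoregressive correlation, three visits: 14.6%, 19.2% and 23.9% at rho 0.5, 0.7 and 0.9. The repeated-measures interaction test then runs slightly high, at 5.2% to 6.0%.
- Larger shifts, interaction without a subject term, rho 0.5 to 0.9: power is 32-42% at 1 SD, 90-98% at 1.5 SD and over 99% at 2 SD.
- Both eyes entered as independent units, no subject term, rho 0.5 to 0.9: group false positives are 26-34% for an assumed between-eye correlation of 0.5, and 32-41% for 0.9. A repeated-measures ANOVA with the eye as its unit still gives about 11-16% for group and 14-22% for interaction.

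**Baseline in the group main effect.** An effect d at both follow-up visits and 0 at baseline averages to (0 + d + d)/3 = 2d/3. This holds for any model that tests the group main effect over all three visits, including a correct mixed model, so it is a separate point from the missing subject term.

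**The case against.** The strongest reply is that the wrong test is inferred. The plan does not describe the 2-way ANOVA as a model without a subject term, nor does it name group and visit as the factors. An author could have used one-way RM-ANOVA or the Friedman test for visits within an arm, and a two-way mixed ANOVA, loosely called 2-way, for the arms. This stands in part: a reader might infer that an invalid test is documented, and it is not. But nothing in the plan rules that test out, and following the named test literally leads to it.

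Three other strong readings also go too far.

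- A reader might take 16-24% as a property of this trial. It depends on an assumed correlation, on three visits and on one value per subject.
- A reader might conclude that the interaction test would detect almost nothing. That fits small shifts (at 0.5 SD, power is 5.5% or less for rho 0.5 to 0.9) but not large ones. Refraction and corneal topography are what the lens is meant to change, and the plan gives no SD to place any endpoint on this scale.
- A reader might suppose that the reported summaries are wrong as well. The plan presents means and standard deviations, which the choice of ANOVA error term does not alter.

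It is also fair to object that adding a subject term for visits alone does not suit data from two eyes. That stands, and the fix below covers it.

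**Conclusion.** The point holds conditionally and should be fixed. What is firm is that the plan names a 2-way ANOVA apart from RM-ANOVA, for subjects measured three times, without factors or a within-subject error term. If it is run as group by visit without a subject term, the p-values are invalid. The group effect is then falsely significant in about 16-24% of trials for an assumed between-visit correlation of 0.5-0.9, or 10-12% at 0.2-0.3. Over the range 0.5-0.9 the interaction test rejects in 0-0.4% of null trials and loses much of its power for small to moderate shifts, while shifts of 1.5 SD or more are still found. If a two-way mixed ANOVA with subject as the unit was meant, these rates do not apply and the gap is one of specification. On either reading, the group main effect over all three visits is a poor measure of treatment, because it includes the pre-lens baseline and shrinks an effect present at both follow-ups to two thirds. The trial's own rates cannot be fixed more closely, because the documents give no correlation, SD or effect size.

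**What to change.** For the group comparison, replace the 2-way ANOVA in the Analysis paragraph with a mixed (split-plot) model:

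- Fixed effects: group, visit and group by visit.
- Subject as a random effect, with the two eyes averaged or nested within subject. Averaging the eyes alone does not repair the handling of visits, and a repeated-measures term for visits alone does not repair the handling of eyes.
- Group tested against between-subject error; visit and group by visit against within-subject error. State the covariance assumption or the sphericity correction.
- Treatment effect read from the group difference in change from baseline (the group by visit term), not from the group main effect.

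The cost is one sentence and a re-run on data already collected, with no new subjects or visits. Some p-values may become less favourable. If a mixed model was already used, the sentence only has to record it and how the eyes were handled.

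### No primary outcome, comparison or time point and no multiplicity method is named, so any of several results at p<0.05, including a before/after change, could carry the effectiveness claim

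*Combined protocol and SAP*

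**What the plan says.** Under Parameters to be assessed, the combined protocol and SAP gives an unranked list: "Effectiveness: Objective and subjective refractive error, central corneal thickness, high contrast visual acuity, low contrast visual acuity, corneal topography". Counting objective and subjective refraction separately, that is six outcomes. Safety measures follow, and then, on its own line, "Subjective evaluation: OSDI Questionnaire".

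The Analysis paragraph covers two kinds of comparison: "Data from both eyes of each subject were analyzed for follow-up visits (within subjects) and for group comparison (between groups". It names three methods, "RM-ANOVA, 2-way ANOVA and Friedman test were used for comparison", without assigning any of them to an outcome or a contrast. It closes with "The significance level is set at p<0.05" and does not say whether tests are one- or two-sided.

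The Protocol section states that subjects consented "before randomly allocating into treatment group (fitting of the contact lenses) or control group (no fitting of contact lens". Controls are examined "at the time point of baseline, 1st month and 3rd month", so two follow-up visits are shared by both groups. Under Sample size, "15 subjects for each group were recruited", with no effect size, SD or power that would point to a main outcome.

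**The concern.** The study sets out to assess effectiveness, but the document does not say which result decides it. Three choices are open: which outcome, which visit (1 or 3 months) and which contrast (within subjects or between groups). There is no success rule and no provision for multiple testing. Two things are at stake.

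- **The contrast.** Subjects are randomised, and only the between-group comparison uses that. As written, a significant change from baseline within the treatment arm would have the same standing as a difference from control. It could carry the claim without the protection that the control group gives.
- **Selection.** If several outcomes are each tested at 0.05, the chance that at least one null outcome reaches nominal significance exceeds 5%. Nothing in this document stops such a result from being given prominence once results are known.

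**Working it through.** **Plan's own figure.** There is none to reproduce. The document states no family-wise error rate, and 15 per group comes without effect size, SD or power.

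**Inputs from the document.** Significance level 0.05 (Analysis); six effectiveness outcomes plus OSDI (Parameters to be assessed); 15 per group (Sample size).

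**Assumptions, not in the document.** Tests are two-sided, with one test per outcome. Each test has a true 5% error rate; how the two eyes are handled is a separate question and is not counted here. Topography counts as one outcome, although no single topography measure is defined. Visits are not multiplied, and safety outcomes are left out. All pairs of test statistics share one correlation ρ, taken as 0, 0.5, 0.7 or 0.9.

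**Number of nulls, k.** If both refraction measures truly change, 6 − 2 = 4 effectiveness outcomes remain: corneal thickness, two acuities and topography. Adding OSDI gives k = 5. If both acuities and topography also truly change, only corneal thickness is left among the effectiveness outcomes (k = 1), or thickness and OSDI (k = 2).

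**Formula.** For independent tests, P(at least one p<0.05) = 1 − 0.95^k. For ρ > 0, with c = 1.96,

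P = 1 − ∫ φ(x) [Φ((c − √ρ·x)/√(1−ρ)) − Φ((−c − √ρ·x)/√(1−ρ))]^k dx.

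At ρ = 0: k = 4 gives 1 − 0.95⁴ = 0.185, and k = 5 gives 1 − 0.95⁵ = 0.226.

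| Null outcomes | ρ=0 | ρ=0.5 | ρ=0.7 | ρ=0.9 |
|---|---|---|---|---|
| Thickness only (k=1) | 5.0% | 5.0% | 5.0% | 5.0% |
| Thickness and OSDI (k=2) | 9.8% | 9.1% | 8.4% | 7.0% |
| Four effectiveness outcomes (k=4) | 18.5% | 15.6% | 13.0% | 9.4% |
| Those four and OSDI (k=5) | 22.6% | 18.3% | 14.8% | 10.2% |

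Simulated two-sample t tests with 15 per group agree: 18.4% and 9.5% for k = 4, and 22.6% and 10.3% for k = 5, at ρ = 0 and 0.9.

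**Both kinds of comparison.** Suppose each of the five nulls (OSDI included) gets a treatment-arm change test and a between-group test, making ten tests. With equal arms and variances, the two tests of one outcome correlate 1/√2 = 0.71. Simulation with 400,000 replicates gives about 35%, 29%, 23% and 16% at the four values of ρ.

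**Price of adjusting secondary outcomes.** For a two-sample t test with 15 per group, the difference detectable with 80% power is 1.06 SD at 0.05. If Holm were applied to six secondary comparisons, its strictest step would be 0.05/6 = 0.0083. There the detectable difference is 1.36 SD, and power for 1.06 SD is about 53%.

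**The case against.** The strongest reply is that the percentages do not measure the harm described. In the main scenario refraction really changes, so a false finding would be on something else, such as corneal thickness, and the trial's main message would still be true. **That stands.** A reader might infer a 9-19%, or even 10-23%, chance of wrongly declaring the lens effective. The document does not support that inference, because it has no success rule from which such a chance could be computed. The higher range also needs OSDI, which the plan lists outside effectiveness.

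Second, the size depends on which outcomes truly change. A lens that changes refraction may well change topography and acuity too, and with corneal thickness as the only null there is no inflation on a one-test-per-outcome basis. **That also stands**, and is why the 5% case belongs beside the range.

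Third, a primary outcome may be recorded elsewhere. The document carries a trial registration number, and Figure 1 is not shown. A primary fixed in the registration would limit later choice, and that cannot be checked here. Figure 1 is captioned as the visit schedule and is unlikely to name one. So the point is confined to what this document fixes. A reader might go further and infer that the headline result was picked after the event; nothing in the text shows that.

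Fourth, the plan does not literally say that every outcome is tested separately. One or more tests per outcome is the natural reading, but it remains a reading.

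None of this answers the point about the contrast. That a within-subject change has the same standing as the randomised comparison follows from the Analysis paragraph and needs no percentage.

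**Conclusion.** The point holds for this document: it does not fix which outcome, contrast or visit decides effectiveness, and it provides no control for multiple tests. The chance of at least one false nominal finding among the effectiveness outcomes is about 9-19% when both refraction measures change and the other four are null. It is 10-23% with OSDI as a fifth null, and 5% when corneal thickness is the only null. These figures rest on one two-sided test per outcome at a true 5% rate and on assumed correlations of 0.9 to 0; the document gives neither the correlations nor the true effects. Testing both contrasts would raise them.

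The weightier part is qualitative: a before/after change in the treatment arm could stand in for the randomised comparison. The plan should be changed, but the defect does not show that any conclusion of the trial is false.

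**What to change.** Name one primary effectiveness analysis at two-sided 0.05. It should compare treatment with control on change from baseline at 3 months, a visit both groups have, in one refraction measure already collected (for example subjective refraction). Use one value per subject, such as the mean of both eyes, so that the test keeps its nominal rate.

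Label all other outcomes, visits and within-subject tests secondary or exploratory, and report them as estimates with 95% CIs. That is enough to answer the point. Only if confirmatory secondary claims are wanted, define one measure per outcome (topography in particular, since the Holm divisor depends on it) and apply Holm after a significant primary.

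**Cost.** If results have not been seen, this is a change of analysis wording only. The primary keeps its full 0.05. Some secondary results lose nominal significance and, if Holm is used, secondary power falls as shown in the working.

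The Sample size and Analysis text is largely in the past tense, which suggests, without proving, that the analysis had been done. If results have been seen, only labelling is open: call the chosen primary post hoc and the other p-values exploratory.

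### Does tying treatment-arm visits to a successful lens prescription remove randomised subjects from the comparison?

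*Combined protocol and SAP*

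**What the plan says.** The first bullet of the Protocol list places consent "before randomly allocating into treatment group (fitting of the contact lenses) or control group (no fitting of contact lens". Fitting is thus what a subject is allocated to, and it follows randomisation.

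The second bullet says "A pair of Breath-O Correct lenses were prescribed for each eligible subject of the treatment group with full wearing instructions of orthokeratology". The third goes on: "After successful prescription of the lenses, the subjects of the treatment group came back for regular visits listed in Figure 1". No criterion for success is given, and no path is described for a subject in whom fitting does not succeed.

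For controls, the last bullet says "For the subjects of the control group, all had the eye examination same as those received by treatment group at the time point of baseline", and adds the first and third months.

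The Sample size line says "15 subjects for each group were recruited". The Analysis paragraph says "Data from both eyes of each subject were analyzed for follow-up visits (within subjects) and for group comparison (between groups". It names RM-ANOVA, two-way ANOVA and the Friedman test, but no analysis population, no replacement rule and no rule for missing visits. The treatment-arm schedule is left to Figure 1, which is not reproduced in the text available here.

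**The concern.** The order of events is the familiar set-up for bias from selection after randomisation. If a subject allocated to lenses cannot be fitted and then has no follow-up visits, that subject contributes nothing after baseline. Nobody in the control arm faces a similar hurdle. The comparison would then be fitted subjects against all controls, and the balance that randomisation gives would be lost.

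For the refractive outcomes the direction is predictable: leaving out subjects with little or no response raises the treatment mean. For safety, which the title names as an aim, the direction cannot be known from the documents. Unfitted subjects may have had almost no lens wear and so resemble controls, or they may have stopped because of a finding at fitting. With 15 subjects per arm, one such subject is 1/15 = 6.7% of the arm.

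**Working it through.** The documents give no effect size, SD, power or fitting-failure rate, so the plan has no figure of its own to reproduce. The check has two parts: what the text says when read in order, and how large the effect could be under stated assumptions.

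**Reading the text in order**

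1. The first bullet speaks of eligible subjects consenting before allocation. Eligibility is settled before randomisation.
2. The second bullet has lenses prescribed for each eligible subject of the treatment group. Given step 1, that is everyone allocated to treatment.
3. The third bullet has the subjects of the treatment group coming back, not a successfully fitted subset. The opening clause then marks when visits start.
4. The control bullet describes the control examinations as the same as those the treatment group received, at baseline and months 1 and 3. That describes parallel follow-up and attaches no fitting condition to it.
5. The Analysis paragraph speaks of each subject and excludes nobody.

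No sentence states that a randomised subject is dropped.

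**Size if some fittings did fail**

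Input from the documents: 15 per group, taken as the number randomised. Assumptions: k = 0 to 3 failures; failures have either no refractive effect or half of it; mean reduction in fitted subjects is 2.50 D, the middle of the usual entry range, (1.00 + 4.00)/2.

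- Ratio of fitted-only to all-randomised mean, no effect in failures: 15/(15 − k)
- The same ratio, half effect in failures: 15/(15 − 0.5k)
- All-randomised mean, no effect in failures: 2.50 × (15 − k)/15

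| k | Ratio, no effect | Ratio, half effect | All-randomised mean (D) | Gap from 2.50 D |
|---|---|---|---|---|
| 0 | 1.000 | 1.000 | 2.50 | 0 |
| 1 | 1.071 | 1.034 | 2.33 | 0.17 |
| 2 | 1.154 | 1.071 | 2.17 | 0.33 |
| 3 | 1.250 | 1.111 | 2.00 | 0.50 |

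**Chance of any failure**

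With failure rate f, the chance of at least one failure in 15 is 1 − (1 − f)^15. For assumed rates of 2%, 5%, 10% and 20% this is 0.261, 0.537, 0.794 and 0.965. The answer depends almost wholly on a rate that the documents do not give.

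**Power, for scale**

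This uses a normal approximation with a two-sided 0.05 level, an assumed true difference of d = 1 SD and one value per subject: power = Φ(d/√(1/15 + 1/n) − 1.96), where n is the number of treatment subjects analysed.

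- No failures, n = 15: Φ(2.739 − 1.960) = 0.782.
- Three failures left out, n = 12: Φ(2.582 − 1.960) = 0.733.
- Three failures kept with no effect, n = 15 and d = 12/15 = 0.80: Φ(2.191 − 1.960) = 0.591.

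Keeping failures would cost some power. That is no reason to exclude them, but it shows that the choice would matter if failures occurred.

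**The case for a change.** The best case for a change is that the timing reading is natural but not secure. Randomised subjects were already eligible, so repeating that word in the second bullet could be a further filter. Calling a prescription successful implies that one could be unsuccessful. The named tests add to the worry: conventional RM-ANOVA and the Friedman test need complete within-subject data, so a subject without visits after fitting would normally drop out by default, without anyone having decided it. A safety finding that ended a fitting could then go uncounted. The remedy would be cheap: a definition, an analysis set and a table of numbers.

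Much of this stands. The term is undefined, the analysis population is unnamed, and the arithmetic is correct given its inputs. What does not stand is the step from silence to a flaw in the design. The plan contains no exclusion, and the control bullet, read to its end, describes matching examinations in both arms rather than unequal follow-up. The Inclusive criteria screen for contra-indications and for willingness to wear the lenses overnight, so failures after allocation should be few. Figure 1 carries the treatment-arm schedule and cannot be seen here, so a claim that follow-up is unspecified cannot be fully tested. The document is also written in the past tense. If conduct is complete, a rule requiring further visits would be moot, and what remains is how subject numbers are reported.

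**Conclusion.** No change to the plan follows. The text leaves a policy unwritten for an event that it never says occurred. It does not prescribe a comparison of fitted subjects with all controls, and its more natural reading is that every treatment subject was prescribed lenses and then followed.

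If no fitting failed, the bias is exactly zero. If one to three failed, had no effect and were left out, the mean refractive change would be overstated by 7% to 25%; with half the effect, by 3% to 11%. These figures rest on assumed failure counts and assumed effects in failures, and the 2.50 D used for the dioptre figures is also an assumption. Nothing shows that any of them would alter a conclusion.

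An analyst would fill the gap in the usual way: report the numbers randomised, fitted and analysed in each arm, analyse available data by allocated group, count safety findings from fitting onwards, and treat any fitted-only result as supportive. The view would change only if those numbers showed treatment subjects lost at fitting and left out of the main comparison.
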